Finally, Phase 1 participants who (1) speak English or Spanish and (2) provide consent to be re-contacted for future research opportunities may be contacted about participation in another study. The research team from Protocol #5790E may reach out to ascertain these participants' interest in completing two standardized measures of the skills and abilities of the adolescent/young adult on the autism spectrum. During the consent process for Protocol #5790E, participants will be informed that their questionnaire data will be linked with the qualitative interviews completed as part of this study. For those families who consent to participate in questionnaires as part of Protocol #5790E, their qualitative data from this study will be shared with the Protocol #5790E research team.

Phase 2: Proof-of-Concept Testing.

Once the program is finalized, 20 families will participate in proof-of-concept testing to assess program acceptability and feasibility. This step is crucial due to the plan to utilize community providers to deliver the program in a telehealth format. Given the small scope of the current project, participating families will need to be fluent in English (not necessarily as a first language) to participate in the trial. The sample will be stratified by race/ethnicity, including approximately equal numbers of families who identify as Black, Latinx of any race, Asian, and non-Latinx white. Parent race/ethnicity will be ascertained during the telephone eligibility screener.

Each service provider will receive in-depth training on the principles and components of the program prior to implementation and will participate in weekly meetings to monitor progress, troubleshoot concerns, and receive intensive consultation on the program. Parents will

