participate in the six- to seven-session program and will complete questionnaires pre- and post-participation. Sessions are designed to be delivered once every 2 weeks, though there will be flexibility with scheduling if families need to hold sessions outside of this window. After each session, program facilitators and family participant(s) will complete a brief open-ended session feedback form, and service providers will upload session recordings to the secure BU site. Family participants (parents/caregivers and youth on the autism spectrum) and service providers will participate in exit interviews to collect overall perceptions of the program, assess program satisfaction, and identify areas for improvement. Individuals on the autism spectrum may provide their feedback in either verbal or written format. Phase 2 measures are expected to take approximately 20 minutes at Time 1 (parents/caregivers) and Time 2 (parents/caregivers, youth on the autism spectrum, and providers). Participating parents also will be asked to participate in six or seven 60-minute program sessions.

Phase 2 data will be collected by BU-based researchers. However, facilitators are also listed as staff because they will be engaged in delivering a research-based program. Please note that facilitators will be considered both staff and participants in this project, and they will be compensated for their time learning and delivering the program.

Families FORWARD Program Description

This is a preliminary description, which will be updated once Phase 1 data collection is complete.

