Session 5: Problem-Solving (P)	
 - Guidance regarding effective problem-solving skills - Normalization of barriers to working toward transition planning goals within or outside schools - Anticipation of potential barriers specific to the family's planning goals (e.g., autism stigma, discrimination, language barriers, immigration considerations) - Practice of problem-solving strategies to address these specific barriers - Revision of program goal to incorporate learning to date
Session 6: Moving Forward (P)	
 - Review of skills and progress made during the program - Creation of a specific action plan for continued work toward planning goals after the program ends that includes long-term goals, proximal goals, and concrete next steps - Proactive identification and problem-solving of any remaining barriers

Telehealth Technology. During the proof-of-concept trial, the Families FORWARD program will be delivered via synchronous videoteleconferencing (VTC) technology. VTC technology enables the secure delivery of interactive meetings that incorporate audio and video streams of data across multiple sites. Based on a review of existing VTC providers and the requirements of

the proposed research, we plan to use Zoom software, a high quality and user-friendly videoconferencing format. Zoom has a HIPAA-compliant version that was developed for use in healthcare settings; this version of Zoom features complete end-to-end 256-bit AES encryption and compliance with HIPAA regulations. The host sends participants a secure link through which to access the meeting/session, and can require a password (provided by the host) to join the meeting; thus, families do not need to register for their own Zoom account. Zoom software clearly identifies the user to the host, after which the host must manually admit the participant to the meeting room. The HIPAA-compliant version of Zoom does not store or retain any session content on a network, which allows providers to comply with HIPAA regulatory guidelines relating to use, disclosure, and storage of confidential information. The HIPAA-compliant version of Zoom allows for local recording by the host (but not by participants), which will allow the research team to review sessions to assess fidelity.

Measures

Phase 1 (Qualitative Interviews) Measures

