Video and audio recordings collected by BU or Lehigh investigators and/or Arc-based program facilitators will be transferred to a password-protected secure network drive at BU and secure cloud storage (when interviews are conducted remotely by BU or Lehigh investigators or Arc providers), and will be deleted from the local laptops. The secure Sharepoint site is maintained by the BU-based research team.

During Zoom sessions, first names only will be used and all family members will be asked to announce themselves at the beginning of the interview to verify that there is no else in the room. All Zoom sessions will be recorded to the BU encrypted, password-protected network drive or a secure SharePoint site for adherence purposes and will be labeled with the unique participant ID number; only researchers specific to the study will be given access to the folder where these

videos are stored, and this access must be provided on an individual case by case basis by the Desktop Services Specialist in BU IT for the Psychology Department. Data collected by both the BU- and Lehigh-based study staff – as well as session recordings being recorded by the Arc-based program facilitators – will be uploaded to a Sharepoint site that is being created and maintained by the BU-based research team.

SECTION N: BENEFITS

Describe the potential benefits to subjects related to the study. State if there are no direct benefits. NOTE: Compensation and/or course credit are not considered benefits.

There are no known direct benefits to participating in this research. Families participating in this research may benefit from individualized support in planning for the transition to adulthood and adult services, which may improve the extent and helpfulness of services obtained into adulthood. Families and service providers may perceive a benefit by knowing that the information provided will assist in the eventual development of better services for culturally-diverse transition-aged youth with autism, for whom there has historically been few evidence-based services.

Describe the potential benefits to society and/or others related to the study

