To assess acceptability, descriptive statistics (mean, median, standard deviation) will be calculated for quantitative acceptability ratings. Exit interview data about program usefulness and value will be evaluated using applied thematic analysis. Analyses will be conducted with the whole sample and separately for each racial/ethnic group. To assess feasibility, we will calculate the number of eligible participants who enrolled in the pilot trial. Retention will be presented descriptively as the average number of sessions completed and follow-up rates within each racial/ethnic group. To assess selective attrition, we will use t-tests and chi squares to evaluate the demographic and autism-related characteristics of families who complete the program vs. those who do not complete the program; these analyses will be conducted for the entire sample. To assess feasibility of the telehealth approach, we will capture technology issues during review of session recordings and will track the number of families who required a tablet to be loaned to them in order to participate in the program.

To assess viability of research procedures and measures, rates of completion for pre- and post-program measures will be described descriptively. We will use t-tests and chi squares to evaluate the demographic and autism characteristics of families who complete the measures vs. those who are lost to follow up; these analyses will be conducted for the entire sample. To assess participant understanding of measures, missing data and inconsistent response patterns will be recorded. Data collection time will be calculated descriptively (mean, standard deviation, range); participant burden regarding completing study measures will be captured qualitatively during exit interviews and will be summarized using applied thematic analysis. Fidelity to the program manual will be assessed by evaluating session recordings against checklists of required components and calculating the percentage of required components present.

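### Review of recordings is the only named source for technology problems during telehealth delivery, so scheduled sessions that leave no recording fall outside that measure

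*Combined protocol and SAP*

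**What the plan says.** The Statistical Analysis Plan, in its paragraph on acceptability and feasibility, gives two measures for the telehealth approach. The study team says "we will capture technology issues during review of session recordings", and it "will track the number of families who required a tablet to be loaned to them". It states no denominator, rate or threshold for technology issues, and no rule for a missing recording.

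Section L (Telehealth Technology) says the chosen Zoom version "allows for local recording by the host (but not by participants), which will allow the research team to review sessions to assess fidelity", and that it keeps no session content on a network. Section L (Phase 2) adds that "service providers will upload session recordings to the secure BU site". Section M states the intended coverage: "All Zoom sessions will be recorded to the BU encrypted, password-protected network drive or a secure SharePoint site for adherence purposes".

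Section L (Phase 2) also describes other contact around each session. "After each session, program facilitators and family participant(s) will complete a brief open-ended session feedback form", and service providers "will participate in weekly meetings to monitor progress, troubleshoot concerns, and receive intensive consultation on the program". Exit interviews follow at the end of the program. Sessions are planned every two weeks, with flexibility to hold them at other times.

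On the reason for the proof-of-concept phase, Section L says: "This step is crucial due to the plan to utilize community providers to deliver the program in a telehealth format".

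**The concern.** A recording reaches the research team only if three things happen: the session connects, the host records it locally, and the provider uploads the file. Technology can break each step. When the first step breaks there is nothing to review, and that is the most complete kind of failure. The named measure therefore sees problems mainly in sessions that worked well enough to be recorded.

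The stakes are modest but real. Telehealth delivery by community providers is a stated reason for running this phase, and the results are meant to guide later work. If the count of technology problems leaves out failed sessions, telehealth delivery may look smoother than it was, and nothing in the planned reporting would show whether that had happened.

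**Working it through.** The plan states no figure for technology issues, so there is nothing to reproduce. The check has two parts: tracing what each planned source would show, and an illustration of size.

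**What each source would show**

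| Event | Recording review | Other planned data |
|---|---|---|
| Session held, recorded, with a problem | Seen | Possibly on the feedback forms |
| Session cut off midway | Possibly seen, if a partial recording is kept and uploaded | Possibly on the feedback forms |
| Session held, but recording or upload missing | Not seen | Feedback forms exist, but are open-ended |
| Session never connected, not made up | Not seen | Lowers sessions completed, without a cause |
| Session never connected, rescheduled and completed | Failed attempt not seen | Sessions completed unchanged; perhaps no form, because the form follows a session |

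Weekly meetings and exit interviews could bring up any of these events. The plan does not name either as a source for technology issues. The tablet count describes access to a device and is the same whatever happens in a session.

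**Illustration of size**

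Inputs from the documents:
- 20 families (Section L, Phase 2).
- Six or seven sessions per family (same section).
- Four or five families per racial/ethnic group (Section J).

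Planned sessions: 20 × 6 = 120 to 20 × 7 = 140. Per group: 4 × 6 = 24 to 5 × 7 = 35.

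Assumed, with no source in the documents:
- f, the share of scheduled sessions lost to technology with no recording.
- g, the share of recorded sessions that show a problem.

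Rate seen in recordings = g. Rate over all scheduled sessions = f + g(1 − f). Understatement = f(1 − g).

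| f | g = 10%: all scheduled | Gap | g = 20%: all scheduled | Gap |
|---|---|---|---|---|
| 0% | 10.0% | 0 | 20.0% | 0 |
| 2% | 11.8% | 1.8 points | 21.6% | 1.6 points |
| 5% | 14.5% | 4.5 points | 24.0% | 4.0 points |
| 10% | 19.0% | 9.0 points | 28.0% | 8.0 points |
| 15% | 23.5% | 13.5 points | 32.0% | 12.0 points |

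Worked case with 120 sessions, f = 5% and g = 10%: 6 sessions are lost and 114 recorded. Problems = 6 + 0.10 × 114 = 17.4, and 17.4 / 120 = 14.5%. The rates are the same with 140 sessions, because the total cancels. Rescheduled attempts raise the total but do not change the formula, provided f is the share of all attempts.

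In a single group, two or three unseen failures would be between 2/35 = 5.7% and 3/24 = 12.5% of its planned sessions.

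The formula applies to sessions lost because of technology. A session left unrecorded for another reason, such as a host who forgot to record, has an unknown problem status. Its absence can make the count of problems too low, but need not shift the rate in either direction.

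**The case against.** The strongest reply is that the study has several other ways to hear of a technology failure, and that a 20-family descriptive phase with no decision rule does not need a formal failure rate. Much of this stands. A session cut off midway may leave a partial recording that shows the problem. A session held but not recorded still has feedback forms. A session never made up lowers the sessions-completed figure. Facilitators meet weekly to resolve difficulties, and exit interviews ask what could be improved. Section M plans to record every Zoom session. The feedback form and the interview guide are not among these documents, and Section L announces an amendment with additional Phase 2 measures, so a technology question may yet be asked.

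A reader might therefore be tempted by stronger conclusions that the documents do not support:
- **That failed sessions leave no data.** The sources just listed contradict this.
- **That telehealth feasibility is overstated.** No failure rate or result is given, and the understatement may be zero.
- **That the loss falls mainly on families with the poorest access.** Nothing in the documents shows this, and the tablet count addresses part of the access question separately.
- **That fidelity is biased upward.** A session that never took place has no fidelity to measure. Only delivered but unrecorded sessions matter, and the direction of their effect is unknown.

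One part of the concern survives the reply. None of the other sources is assigned to record technology as a cause, and a failed attempt that is rescheduled and then completed leaves no trace in any planned measure.

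**Conclusion.** The point holds as a gap in measurement. Recordings are the only source named for technology issues during delivery, and sessions without a recording fall outside that measure. Technology problems may be understated; where sessions are lost to technology, the error can only favour telehealth. The amount is unknown. Over the assumed range (f from 2% to 15%, g of 10% or 20%) it is about 1.6 to 13.5 percentage points, and it is zero if no session is lost without a recording. As written, the plan has no means of showing which case applies.

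This is a cheap improvement to a descriptive outcome. It is worth making because telehealth delivery is a stated reason for the phase. It does not undermine the trial.

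**What to change.** 1. Have the facilitator log every scheduled session as held, cut short, rescheduled, not held or not recorded, with technology as the cause marked yes or no.
2. Add one technology item to the form that facilitators already complete after each session.
3. Report technology issues over all scheduled sessions, counting rescheduled attempts, and keep review of recordings as a supplement. Continue to report tablet loans as a measure of device access.
4. Beside the fidelity percentage, give the number of delivered sessions without a usable recording.

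The amendment announced for Phase 2 measures is a natural place for the log and the item. Both should be in use from the first session, because causes are hard to recover afterwards. The cost is about a minute of facilitator time per session and a rate that may look less favourable than one drawn from recordings alone.

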*****All consent forms are stored on REDCap platform*****
